Appendix D. Medication Diary

Participant ID _____ Study physician _____

Instructions: This is a checklist for you to use to record taking your study drug. Please put a check mark beside each day as you take the study drug. Remember: Please take the drug 1 hour before or 2 hours after eating. Use the back side of this chart to record any side effects or symptoms you experience.

Date	Time study drug was taken	Fasting?	Date and Time of last meal	Any New Medications? Please list. Use the back of this page if needed.
Example: Day 0 Date: 9/6/2016	5:30 am	√ Yes	9/5/2016 7:00 pm	Ibuprofen for headache, 2:00 p.m., okay by 3:00 p.m.
 Day 1 Date _____				
 Day 2 Date _____				
 Day 3 Date _____				
 Day 4 Date _____				
 Day 5 Date _____				
 Day 6 Date _____				
 Day 7 Date _____				
 Day 8 Date _____				
 Day 9 Date _____				
 Day 10 Date _____				
 Day 12 Date _____				
 Day 13 Date _____				
 Day 14 Date _____				

Participant Signature _____ Date _____

Study Coordinator Signature _____ Date _____

Symptoms: Please list any side effects or symptoms you experience. If possible, note the date the symptoms started and the date they disappeared.

Appendix E. Schema Summary

Schema Describing Dose Level Assignment

MTD: Maximum Tolerated Dose

DLT: Dose Limiting Toxicity

Safety is defined as < 33% DLT.

Efficacy is defined as $\geq 40\%$ demonstrate reduction in EGFR staining,

Enrollment will be in cohorts of 5 as described in Section 7.4.2. Accrual will be temporarily halted after each cohort of 5 to evaluate safety and efficacy.

Stage 1 (75 mg/day)

Enroll 10

- If safe but not effective, go to Stage 2
- If safe and effective, go to Stage 4
- If not safe but effective, go to Stage 4
- If not safe and not effective, **end study**.

Stage 2 (100 mg/day)

Enroll 10

- If safe but not effective, go to Stage 3.
- If safe and effective, declare 100 mg/day a safe dose and enroll expansion cohort at 100 mg/day.
- If not safe but effective, declare 75 mg/day a safe dose and enroll expansion cohort at 75 mg/day.
- If not safe and not effective, pool data from Stages 1 and 2 to determine whether or not $\geq 40\%$ demonstrate reduction in EGFR staining (definition of effective). If still not effective, **end study**. If effective, declare 75 mg/day a safe dose and enroll expansion cohort at 75 mg/day.

Stage 3 (150 mg/day)

Enroll 10

- If safe but not effective, **end study**.
- If safe and effective, declare 150 mg/day a safe dose and enroll expansion cohort at 150 mg/day.
- If not safe but effective, pool data from Stages 2 and 3 to determine whether or not $> 33\%$ demonstrate a DLT. If total % DLT is $< 33\%$, declare 100 mg/day a safe dose and enroll expansion cohort at 100 mg/day.
- If not safe and not effective, pool data from Stages 2 and 3 to determine whether or not $\geq 40\%$ demonstrate reduction in EGFR staining (definition of effective). If still not effective, **end study**. If effective, declare 100 mg/day a safe dose and enroll expansion cohort at 100 mg/day.

Stage 4 (50 mg/day)

Enroll 10

- If safe and effective, go to Stage 5.
- If safe but not effective, declare 75 mg/day a safe dose and enroll expansion cohort at 75 mg/day.
- If not safe but effective, pool data from Stages 1 and 4 to determine whether or not $> 33\%$ demonstrate a DLT. If total % DLT is $< 33\%$, declare 50 mg/day a safe dose and enroll expansion cohort at 50 mg/day.
- If not safe and not effective, pool data from Stages 1 and 4 to determine whether or not $\geq 40\%$ demonstrate reduction in EGFR staining (definition of effective). If still not effective, **end study**. If effective, declare 75 mg/day a safe dose and enroll expansion cohort at 75 mg/day.

Stage 5 (25 mg/day)

Enroll 10

- If safe but not effective, declare 50 mg/day a safe dose and enroll expansion cohort at 50 mg/day.
- If safe and effective, declare 25 mg/day a safe dose and enroll expansion cohort of 20 at 25 mg/day.
- If not safe but effective, pool data from Stages 4 and 5 to determine whether or not > 33% demonstrate a DLT. If total % DLT is < 33%, declare 25 mg/day a safe dose and enroll expansion cohort at 25 mg/day.
- If not safe and not effective, pool data from Stages 4 and 5 to determine % DLT and % reduction in EGFR staining (definition of effective). If safe, enroll expansion cohort at 25 mg/day.

Minimum enrollment = 10; if 75 mg/day deemed not safe (after < 3 cohorts of 5) and not effective.

Maximum enrollment = 45; if 25 mg/day deemed safe and expansion cohort enrolled.

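### Appendix E can declare 75 mg/day safe and expand it after 75 mg/day itself breached the 33% DLT limit, and can clear a lower dose that breached it by pooling DLTs with the next higher dose

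*Combined protocol and SAP*

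**What the plan says.** Appendix E gives its own criterion: "Safety is defined as < 33% DLT". Section 7.4.2 applies the same limit dose by dose, to everyone enrolled at that dose. A dose at or above 33% is over the MTD whatever its staining result. Sections 3 and 13.4 place the expansion cohort at the MED, and Section 8.1 asks for a dose that is both safe and minimally effective.

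The branches of Appendix E that matter are these.

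- Stage 1 (75 mg): "If not safe but effective, go to Stage 4".
- Stage 4 (50 mg), safe but ineffective: "If safe but not effective, declare 75 mg/day a safe dose and enroll expansion cohort at 75 mg/day".
- Stage 4, unsafe and ineffective: staining is pooled over Stages 1 and 4, and then "If effective, declare 75 mg/day a safe dose and enroll expansion cohort at 75 mg/day".
- Stage 4, unsafe but effective: "If not safe but effective, pool data from Stages 1 and 4 to determine whether or not" DLTs exceed 33%. If they are below 33%, 50 mg is declared safe and expanded.
- Stage 5 (25 mg), unsafe but effective: DLTs are pooled over Stages 4 and 5, and "If total % DLT is < 33%, declare 25 mg/day a safe dose and enroll expansion cohort at 25 mg/day".
- Stage 5, unsafe and ineffective: DLTs and staining are both pooled, but expansion of 25 mg is made conditional on safety only.

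Sections 7.4.3 and 13.8 judge efficacy by at least 2 responses in the first 5 evaluable participants, with the dose deemed safe. The closing MED sentence of 7.4.3 asks for at least 40% of the evaluable participants at the dose and mentions no safety condition.

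**The concern.** The output of this algorithm is the primary endpoint, and Section 2.3 expects the result to set the dose schedule for later randomized studies. Read literally, Appendix E can attach the word safe to a dose that 7.4.2 has just placed above the MTD, and then enroll more participants with cirrhosis at that dose. It can also let a dose pass on another dose's DLT record. Nothing in the protocol says whether Appendix E or Section 7.4.2 prevails.

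**Working it through.** **1. The plan's own figure.** Section 13.4 gives 91% for at least 2 responses in 5 at a true rate of 60%. From its table, 1 − 0.010 − 0.077 = 0.913, so it reproduces. The points below do not change it.

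**2. The limit in counts (7.4.2).** 0–1 DLT of 5 is safe. 2–3 of 5 adds five participants, and the dose is then unsafe at 4 or more of 10 (3/10 = 30%, 4/10 = 40%). 4–5 of 5 is unsafe.

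**3. Stage 4, safe but ineffective.** Suppose 75 mg has 4/10 DLTs (unsafe) and 2/5 responses (40%, effective), so Stage 1 goes to Stage 4. There 50 mg has 0/5 DLTs (safe) and 1/5 responses (20%, ineffective). Appendix E declares 75 mg safe and expands it at its own 40% DLT rate. On the other route into Stage 4, 75 mg has already passed its DLT check, so the fault is confined to the unsafe-but-effective route.

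**4. Stage 4, unsafe and ineffective.** Suppose both doses have 4/10 DLTs, with 3/5 responses at 75 mg and 1/5 at 50 mg. Pooled response is (3 + 1)/10 = 40%, so 75 mg is declared safe although both doses breached the limit.

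**5. Pooled-DLT clearance.** With 0/10 at 75 mg and 4/10 at 50 mg, the pooled rate is 4/20 = 20%, so 50 mg is cleared at its own 40%. Stage 5 works the same way with 50 mg and 25 mg. A pooled rate is a weighted average, so two doses that each breach the limit cannot pool below it. Clearance therefore needs the higher dose to have been safe. No action is stated if the pooled rate is 33% or more.

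**6. Stage 5, unsafe and ineffective.** Stage 5 is entered only if 50 mg was safe and effective. With the same counts (0/10 and 4/10), pooled DLT is 20% and 25 mg is expanded after failing both tests, while 50 mg had passed both.

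**7. How often step 3 could occur.** The documents give no DLT rates for cirrhosis, so every rate here is an assumption.

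- At 50 mg, assume 10% DLT, so P(unsafe) = 0.010 under step 2, and true response of 40% or 20%, so P(≥2 of 5) = 0.663 or 0.263. Given arrival from an unsafe 75 mg, the faulty branch follows with probability 0.990 × 0.337 = 0.334 to 0.990 × 0.737 = 0.730.
- At 75 mg, assume 60% response. Treat DLT participants as non-evaluable (5.6 stops their dosing, and 5.7.1 requires the procedure-day dose). Being unsafe with 5 evaluable then needs exactly 4 or 5 DLTs in 10. At a 40% true DLT rate, with 2 or 3 DLTs in the first five, these have probability 0.3456² + 0.2304 × 0.2592 = 0.179 and 2 × 0.3456 × 0.2304 = 0.159. With no other loss, P(unsafe and effective) = (0.179 + 0.159) × 0.913 = 0.309.
- With 30% other loss (13.3's 30–40%, taken as non-DLT loss), at least 5 remain evaluable with probability 0.7⁶ + 6 × 0.7⁵ × 0.3 = 0.420 and 0.7⁵ = 0.168. The joint value is (0.179 × 0.420 + 0.159 × 0.168) × 0.913 = 0.093. With 40% loss it is 0.049.

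Multiplying by 0.334 to 0.730 gives the probability that an unsafe-graded 75 mg is declared safe through step 3:

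| True DLT rate at 75 mg | 30–40% other loss | No other loss |
|---|---|---|
| 20% | 0.5–2.0% | 2.6–5.6% |
| 30% | 1.2–4.9% | 6.8–15% |
| 40% | 1.7–6.8% | 10–23% |

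If DLTs cost no evaluability, the 40% row becomes 0.529 × 0.913 × (0.334 to 0.730) = 16–35%. Only the 40% row describes a truly unsafe dose. The other rows are breaches of procedure. With no DLTs the probability is zero.

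**8. The closing sentence of 7.4.3.** With exactly 5 evaluable it agrees with 13.8. If it means all evaluable participants, 2 responses in the first five and none later gives 2/6 = 33% or 2/7 = 29%, which passes 13.8 and fails 7.4.3. At true response 40% and 60%, the probability is 0.3456 × 0.6 = 21% and 0.2304 × 0.4 = 9% with 6 evaluable, and 0.3456 × 0.36 = 12% and 0.2304 × 0.16 = 4% with 7.

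**The case against.** The strongest reply is that the body text already settles safety. Appendix E is a summary. Section 7.4.2 is explicit, and the MED declarations in 7.4.3 and 13.8 each require a safe dose. Reopening after a pause needs consultation with the medical monitor, who could catch the conflict. This reduces the risk but does not remove the contradiction, because no clause gives the body text precedence and Appendix E is the only place that spells out every branch.

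It is also fair that steps 3 to 6 all need an unsafe dose, and that steps 5 and 6 need a lower dose to look more toxic than a higher one. Amendment 9 reports no DLTs. The Stage 5 branch does pool staining, so its safety-only condition may be incomplete drafting.

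Three stronger readings are tempting, and the documents do not support them.

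- A reader might infer that an unsafe dose was in fact advanced. The Amendment 9 note rules this out up to that point.
- A reader might infer that Stages 2 and 3 name a failed dose as the MED, since "If not safe but effective, declare 75 mg/day a safe dose and enroll expansion cohort at 75 mg/day" follows a Stage 1 in which 75 mg failed efficacy, and Stage 3 ("If not safe but effective, pool data from Stages 2 and 3 to determine whether or not" DLTs exceed 33%) can expand 100 mg after it failed efficacy. Appendix E calls these safe doses, not MEDs, and falling back to the lower dose as the MTD agrees with 7.4.2. What is missing is a label.
- A reader might infer from the last sentence of 7.4.3 that the MED has no safety condition or that two rival rules exist. Safety is required elsewhere, and the sentence can be read as meaning the first five evaluable. It needs clarifying, and choosing the first five over all evaluable participants is partly a preference.

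**Conclusion.** The contradiction is in the text. Two Stage 4 branches can declare 75 mg safe and expand it after its own DLT rate reached 33% or more. Stages 4 and 5 can clear a dose that breached the limit by borrowing a higher dose's record. Stage 5 can expand 25 mg after it failed both tests. These conclusions rest only on the wording of Appendix E and 7.4.2. The probabilities, from under 1% to about a third, rest on assumed DLT and response rates and should be read only as showing that the faulty route is reachable. Because no DLTs were reported by Amendment 9, nothing suggests that any dose decision was affected. Severity is minor to should-fix: an internal contradiction in the dose rule. The MTD label in Stages 2 and 3 and the closing sentence of 7.4.3 are secondary wording points.

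**What to change.** Add to Appendix E: *A dose whose own DLT rate is 33% or more under 7.4.2 is not declared safe and not expanded.* Then:

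- In both Stage 4 branches that name 75 mg, return to 75 mg only if it was safe in Stage 1. Otherwise end with no safe MED found.
- Remove the pooled-DLT clearance in Stages 4 and 5 and apply 7.4.2 to the dose's own participants. If 50 mg is unsafe but effective, suspend for medical monitor review and state the outcome; the same return rule for 75 mg would serve.
- If 25 mg is unsafe, whether or not it is effective, expand 50 mg, which was safe and effective in Stage 4, subject to medical monitor review.
- Secondary: where 100 or 150 mg is unsafe but effective, label the lower-dose expansion as at the MTD, not the MED. In the closing sentence of 7.4.3, add that the dose is deemed safe under 7.4.2 and that the participants meant are the first 5 evaluable, to match 13.8.

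The cost is wording in Appendix E and one sentence of 7.4.3, with no added participants or procedures. The change does add a no-safe-MED ending, and as an amendment it needs DCP and IRB approval before use (14.3), at a time when 13.3 says the study agent is close to expiry.

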The first dose level will consist of an intermediate dose of erlotinib (75 mg/day). It was considered ideal to choose a starting dose with room for both escalation and de-escalation depending upon reported adverse events and efficacy. This starting dose is less than that prescribed for treatment of cancer (150 mg/day), and is the human equivalent of a dose demonstrated to have efficacy in a rat model of cirrhosis and HCC (7). If the end-point (reduction of phospho-EGFR staining) is not achieved at this initial dose level, and the dose level is deemed safe, the next dose level consists of a higher dose of erlotinib. Conversely, if the primary end-point is achieved at this initial dose level, and the dose level is deemed safe, then the next dose level consists of a lower dose of erlotinib. It is probable that this algorithm will determine the minimum effective dose (MED) with fewer participants than alternative algorithms of starting at the lowest dose and escalating, or starting at the highest dose and de-escalating. Once the minimum effective dose (MED) is defined by this algorithm, an expansion cohort of 20 (to obtain 10 evaluable participants) will be enrolled to improve statistical confidence of the observed response rate. See Section 13 for details on the study design and the endpoints. The maximum dose for this trial will be 150 mg/day, taking into account the observation that this dose level has proven safe in oncology patients, but simultaneously the side effects associated with this dose level are likely considered excessive for long term use as chemoprevention. See Sections 5.1 and 5.2 for dose level information. See Section 7.4.2 for description of determination of safe/maximum tolerated dose.

Participants will take erlotinib at their assigned dose level for 7 days (acceptable range = 5 days to 14 days) leading up to the morning of their scheduled liver resection or liver biopsy. Participants will be contacted by study personnel on the third day to obtain information on adverse effects and to ascertain compliance. If surgery or biopsy is delayed and treatment extends beyond 7 days, then an additional

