13.3 Accrual and Feasibility

Ten participants will be enrolled (in cohorts of 5) at each dose level to reach the goal of 5 evaluable participants in each dose level using a cohorts-of-5 design. This assumes that 30%-40% of participants will not be evaluable for the primary endpoint for the surgical cohort, have no phospho-EGFR staining (i.e. no positive pixels, see Section 9.0) at baseline, for both cohorts, will otherwise be non-evaluable (drop-out, non-compliant etc.). Assuming that 10 participants are required at each dose level (to achieve the desired 5 evaluable participants), and assuming the theoretical maximum of 3 dose levels, a total of 30 participants may be required for the dose escalation phase to determine the MED. An additional 15 participants will be accrued to the MED in the expansion cohort, wherein we again assume that 30%-40% of participants will not be evaluable for the primary endpoint (see rational above), thus leading to 10 evaluable participants. See section 13.6 for the details on criteria for evaluability of primary endpoint. Thus, the maximum accrual to this trial may be 45 (30 for dose escalation and 15 for the expansion) in order to accrue 25 evaluable participants.

Update with Amendment 9: Because there were no dose-limiting toxicities and there were sufficient numbers of evaluable participants, none of the cohorts were repeated. The target accrual has been adjusted from the original “up to 65” downward to 31. The accrual time frame is limited due to the imminent expiration of the supply of study agent.

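### The expansion cohort is 20 in Section 3 and Appendix E but 15 in Section 13.3, and Appendix E's maximum of 45 does not follow from its own stages, which sum to 50

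*Combined protocol and SAP*

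**What the plan says.** Four places give the size of the expansion at the minimum effective dose (MED), each aiming at 10 evaluable participants:

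- Section 3: "an expansion cohort of 20 (to obtain 10 evaluable participants) will be enrolled".
- Appendix E, Stage 5, if safe and effective: "declare 25 mg/day a safe dose and enroll expansion cohort of 20 at 25 mg/day". The other expansion branches of Appendix E give no number.
- Section 13.3: "An additional 15 participants will be accrued to the MED in the expansion cohort", with the reasoning that "30%-40% of participants will not be evaluable for the primary endpoint (see rational above), thus leading to 10 evaluable participants".
- Section 13.4: accrual at the selected dose rises to 20 in all, again for 10 evaluable. The next paragraph but one of that plan gives a two-sided 90% confidence interval (CI) with a margin of roughly 25% for 10 evaluable.

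Two places give a maximum. Section 13.3 says "the maximum accrual to this trial may be 45 (30 for dose escalation and 15 for the expansion", and continues "in order to accrue 25 evaluable participants". Appendix E says "Maximum enrollment = 45; if 25 mg/day deemed safe and expansion cohort enrolled".

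The enrolment per dose level also differs. Sections 13.3 and 13.8 and every stage of Appendix E use 10. Section 7.4.3 uses 15 at levels +1 and +2.

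The Amendment 9 update in Section 13.3 says "none of the cohorts were repeated. The target accrual has been adjusted from the original" ceiling of 65 to 31. It does not split the 31 between dose finding and expansion.

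**The concern.** These are the sample-size figures the trial runs on, and they stand in current text, not in a change log. A site or statistician following Section 3 would plan a different expansion from one following Section 13.3. Appendix E contradicts itself.

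The expansion size also drives how many evaluable participants can be expected. The CI in Section 13.4 is the plan's only precision statement for the expansion response rate, and the results are meant to inform a larger study. The same 10 evaluable cannot be the expected yield of both 15 and 20 under one loss assumption.

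**Working it through.** **Maxima.** Inputs: 10 per stage (Appendix E, 13.3, 13.8); three dose levels at most (13.3; in Appendix E the route is Stages 1, 4 and 5); expansion of 15 (13.3) or 20 (Section 3, Appendix E Stage 5).

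- Section 13.3: 3 × 10 + 15 = 45 enrolled, and 3 × 5 + 10 = 25 evaluable. Both stated figures reproduce.
- Appendix E: 10 + 10 + 10 + 20 = 50, against a stated 45.
- If the 20 already includes the 10 of the last stage: 30 + 10 = 40, which is not 45 either.
- Neither 45 nor 50 is an absolute ceiling, because 7.4.3 allows further groups of 5 when fewer than 5 are evaluable.

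**Expected evaluable.** With loss d, the yield is N × (1 − d). For 15 enrolled to give 10, d must be at most 1 − 10/15 = 33%. For 20 enrolled to give exactly 10, d is 50%, outside the 30-40% assumed. The chance of at least 10 is P(Binomial(N, 1 − d) ≥ 10), taking losses as independent. The last column is the 90% Wald half-width at the expected yield n, 1.645 × √(0.25/n), with a response rate of 50%.

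| Enrolled | Loss | Expected evaluable | Chance of at least 10 | 90% half-width |
|---|---|---|---|---|
| 15 | 30% | 10.5 | 72% | 25.4 points |
| 15 | 40% | 9.0 | 40% | 27.4 points |
| 20 | 30% | 14.0 | 98% | 22.0 points |
| 20 | 40% | 12.0 | 87% | 23.7 points |

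**The plan's margin.** For n = 10 the Wald half-width is 1.645 × √(0.4 × 0.6/10) = 25.5 points at a rate of 40% or 60%, and 26.0 at 50%. The stated margin of about 25% therefore reproduces. The exact (Clopper-Pearson) half-width is 27.3 to 27.8 points for 4 to 6 responders. With 9 evaluable and 4 or 5 responders it is 27.2 Wald or 29.0 exact.

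**Amendment 9.** What remains of 31 for expansion depends on figures the documents do not give:

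- 5 per level at three or two levels: 31 − 15 = 16, or 31 − 10 = 21.
- 10 per level at three or two levels: 31 − 30 = 1, or 31 − 20 = 11.

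The possible expansion thus runs from 1 to 21.

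**The case against.** The strongest objection is that events have overtaken the conflict. Amendment 9 makes 31 the operating target, so 45 against 50 changes little enrolment. That stands, and it lowers the severity. It does not remove the conflict, and it leaves the expansion share of the 31 unstated.

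Second, the fall in the chance of reaching 10 evaluable, to 40%, looks worse than it is. A reader might infer that the interval fails if 10 is missed. It does not: at a rate of 50%, 9 evaluable instead of 10 widens the Wald half-width from 26.0 to 27.4 points, which matters little in a pilot. This stands too.

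Third, a reader might infer that the interval is biased because it includes the five participants who passed the 2-of-5 rule. The documents do not support this. In 13.4 the 10 evaluable behind the interval come straight after the 10 the expansion is to provide, and 13.3 reaches 25 evaluable by adding 10 to the 15 from dose finding. Newly enrolled participants are the natural reading. What remains is that 13.4 does not say so, and 20 in all at the dose could be read to include the five. The margin cannot settle it, since 5 + 5 also makes 10. Section 3's aim of firming up the observed response rate could also describe pooling, and pooling 5 with 10 new would narrow the interval to about 21 points Wald. That choice is partly a trade-off.

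Fourth, a reader might attach a chance of reaching 10 evaluable to the target of 31. No single figure is supportable. An unrepeated cohort of 5 implies, under 7.4.3, that all five were evaluable, which sits badly with applying 30-40% loss to the rest; with 10 per level only 11 or 1 remain.

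Finally, the 15 in 7.4.3 might be a ceiling of three cohorts of 5, though it is worded as enrolment. The superseded 65 equals 3 × 15 + 20, so the 15s per level and the 20s may be leftovers. That is inference, and the figures still stand as instructions.

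**Conclusion.** The enrolment figures conflict as written: expansion 20 against 15, Appendix E's maximum 45 against its own sum of 50, and 15 against 10 per higher dose level. This rests on simple sums of the plan's numbers and is certain.

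The claim that 15 enrolled lead to 10 evaluable holds only if loss is at most 33%, which covers part of the assumed 30-40%. The cost in precision is modest: a half-width of about 25-27 points from 15 enrolled against 22-24 from 20, assuming independent losses and a response rate near 50%.

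With the target now 31, the point is minor. It is a matter of reconciling text and stating the expansion share. It gives no reason to think the primary analysis is invalid.

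**What to change.** - Reconcile Sections 3, 7.4.3, 13.3, 13.4, 13.8 and Appendix E to one per-level size, one expansion size and one maximum. With 10 per level, Appendix E's total is 50 with an expansion of 20 and 45 with 15. Say that further groups of 5 under 7.4.3 can raise it.
- State how many of the Amendment 9 target of 31 are expansion participants.
- Restate the expected evaluable number at 30-40% loss and the CI margin for that expansion size. If only 9 are evaluable, the margin is about 27 points Wald or 29 exact.
- As a minor clarification, say in 13.4 whether the 10 evaluable are newly enrolled participants only or include the five used to select the dose. If they are pooled, note that those five were selected by their responses.

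The cost is wording only. The one downside is a slightly wider stated margin if 15 is kept.
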